7.5.5 Analysis of Objective Response

The number and percentage of subjects in each category of best overall response per IRC (stringent complete response [sCR], complete response [CR], very good partial response [VGPR], partial response [PR], minor response [MR], stable disease [SD], progressive disease [PD], or unable to determine [UD]) according to the IRC will be presented, by treatment group. An estimate of the response rate and an associated exact two-sided 95% CI (Clopper and Pearson¹⁴) will be presented, by treatment group. Also, the number and percentage of subjects in each category of best overall response according to the investigator tumor assessment will be presented by treatment group.

The main analysis of ORR will be based on the IRC assessment and will compare the two treatment groups using a CMH test stratified by the same factors used in the analysis of PFS. An estimate of the treatment odds ratio and corresponding two-sided 95% CI will be presented.

The same analysis will be repeated for the best response per IRC but modified for subsequent therapies. For this analysis only subjects with responses before, or on start of subsequent therapy date will be considered responders. The IRC when doing the blinded assessment of response and progression does not have data on subsequent therapy and discontinuation status. For this reason the IRC best response modified for subsequent therapy will be derived programmatically.

A 2-sided, 95% confidence interval for the difference of ORR between treatment arms will be computed for all randomized subjects by the method of DerSimonian and Laird¹⁵ using a fixed-effects model (setting Δ^2 equal to zero), adjusting for the stratification factors. The weighted response rate difference and 95% CI can be determined using the following formula:

$$\hat{\theta} = \frac{\sum_{i=1}^{12} \hat{\theta}_i w_i}{\sum_{i=1}^{12} w_i} \sim N(\theta, 1 / \sum_{i=1}^{12} w_i)$$

where $\hat{\theta}_i$ is the response rate difference of the i^{th} stratum and $w_i = 1/\text{var}(\hat{\theta}_i)$.

Similar analyses will be repeated based on the investigator's assessment of ORR. A cross tabulation of IRC best response versus the investigator best response will be presented, by treatment group. These measures of concordance will be provided:

- Number of subjects with same response divided by number of randomized subjects
- Number of subjects with same response evaluation: responders (PR or better), non-responder divided by number of randomized subjects

[REDACTED]

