2.2 Treatment Assignment

After a subject's eligibility for randomization is established and informed consent has been obtained, the subject's treatment will be assigned via an interactive voice response system (IVRS). Subjects will be randomized to Ld or E-Ld in a 1:1 ratio. The randomization will be stratified by:

- Stage of disease (International Staging System (ISS) 1 - 2 versus 3)
- Age (< 75 years old versus \geq 75 years old)
- Eastern Cooperative Oncology Group (ECOG) Performance status (0 versus 1 - 2)

and will be carried out via permuted blocks within each stratum.

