7.5 Efficacy

Efficacy analyses (PFS, ORR and OS) will be conducted on the population of all randomized subjects, grouped by arm assigned at randomization, unless otherwise noted.

The main analyses of PFS and ORR will be based on IRC evaluation. Unless stated otherwise, whenever a stratified analysis is specified, the stratifications factors will be those used in the randomization (per IVRS), that is:

- Stage of disease (ISS 1 – 2 versus 3)
- Age (< 75 years old versus \geq 75 years old)
- ECOG Performance status (0 versus 1 - 2)

All p-values reported will be two-sided. Confidence intervals (CI) for the PFS and OS endpoints will be based on the nominal significance level adjusted for the interim analyses to preserve the overall type I error rate. Two-sided 95% CI will also be provided. CIs for the other endpoints will be at the two-sided 95% level. The p-values presented in the clinical study report will be rounded to the fourth decimal place. Point estimates and confidence bounds for efficacy variables will be rounded to the second decimal place.

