where $i=1-8$ corresponds to each of the eight levels the stratum can take, and Z is the treatment indicator, which is equal to 1 for the experimental combination arm and 0 for the control arm. The transformation of time that will be used is $\log(t)$. The null hypothesis, that the proportional hazards assumption is valid, i.e., that $b_2=0$, will be tested against the alternative hypothesis that $b_2 \neq 0$ using a Wald statistic.

[REDACTED]

[REDACTED]

[REDACTED]

[REDACTED]

[REDACTED]

[REDACTED]

[REDACTED]

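### The stratified ORR-difference formula in SAP 7.5.5 sums over 12 strata where the design has 8, and its inverse-variance weights have no rule for a stratum with zero variance; the effect is minor and confined to a supplementary interval

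*SAP*

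**What the plan says.** SAP 7.5.5 makes the stratified CMH test, based on review-committee assessments, the main ORR comparison, with an odds ratio and its 95% interval. It then adds a second estimate: "A 2-sided, 95% confidence interval for the difference of ORR between treatment arms will be computed for all randomized subjects", by the DerSimonian and Laird method "using a fixed-effects model". The estimate is "adjusting for the stratification factors. The weighted response rate difference and 95% CI can be determined using the following formula". In that formula the sums in the numerator, the denominator and the variance all run from i = 1 to 12, and each weight is the reciprocal of the variance of that stratum's rate difference. The section repeats similar analyses for investigator-assessed response.

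SAP 7.5 fixes the factors: "whenever a stratified analysis is specified, the stratifications factors will be those used in the randomization (per IVRS". SAP 2.2 and protocol sections 3.1 and 4.2 list three, each with two levels: ISS stage (1-2 or 3), age (under 75, or 75 and over) and ECOG status (0 or 1-2). SAP 7.5.1, on the proportional-hazards check for PFS, says that its stratum index "corresponds to each of the eight levels the stratum can take".

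The visible text of 7.5.5 names no variance estimator for the stratum differences. It gives no continuity correction, no pooling of strata, and no rule for a stratum with zero variance or an empty arm.

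**The concern.** Two separate things look wrong. The printed index disagrees with the design and with another section of the same SAP. And a formula that divides by an estimated variance fails when that estimate is zero, which can happen in a small stratum when response rates are high. With no rule written down, the analyst would have to choose one after seeing the data, in an open-label trial.

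There is also a calibration question. The interval treats the weights as known, but they are computed from the same response counts as the differences they weight. A stratum whose observed rates happen to be extreme gets a small estimated variance and too much weight, so the interval can be too narrow.

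What is at stake is whether the reported ORR difference and its interval can be computed as specified and have the stated coverage.

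**Working it through.** **Number of strata.** Three factors with two levels each (SAP 2.2) give 2 x 2 x 2 = 8. The printed 12 cannot be reproduced from these factors. It appears three times in the formula, so it is not a single slip of one symbol. Only eight strata can exist in the data, so there are no terms 9 to 12 to add and the result is the same under either index.

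**Zero variance.** Take the usual unpooled binomial variance (an assumption, since the SAP names none): var = p1(1-p1)/n1 + p0(1-p0)/n0. With 6 of 6 responders in each arm, var = 1 x 0/6 + 1 x 0/6 = 0, so the weight is 1/0. The pooled form also gives 0, because the pooled rate is 12/12 = 1. The same holds when nobody responds in either arm.

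**How often.** Inputs from the documents are about 750 subjects, 1:1 allocation and 8 strata. Stratum sizes and ORRs are assumptions. For one stratum with n per arm, P(all respond in both arms) = (pc x pt)^n, with pc and pt the control and experimental response rates:

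| n per arm | 70% v 70% | 70% v 80% | 80% v 88% |
|---|---|---|---|
| 6 | 0.49^6 = 1.4% | 0.56^6 = 3.1% | 0.704^6 = 12.2% |
| 47 (750/16, equal strata) | about 0 | about 0 | about 0 |

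Simulating whole trials (40,000 per scenario, which adds the contribution of the other seven strata) gave 0% with large strata and 1.5-13% with 6 per arm in the smallest stratum, for ORR of 70-88%. Other assumptions move the figure a long way:

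| Smallest stratum, per arm | 70% v 80% | 80% v 90% |
|---|---|---|
| 11 | 0.2% | 3.0% |
| 6 | 3.2% | 15.5% |
| 3 | 20% | 44% |

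**Coverage.** The estimate is sum(w d)/sum(w), where d is the stratum difference, and its standard error is 1/sqrt(sum w). With equal response rates across strata and ORR of 70-88%, the SAP interval covered 94.0-94.4%, a shortfall of 95 - 94.4 = 0.6 to 95 - 94.0 = 1.0 points. Over ORR pairs from 50 v 60% to 80 v 90%, coverage was 93.7-94.4%. With eight equal strata and ORR up to 80 v 90%, where zero variance essentially never occurred, coverage was still 93.9-94.4%. Dropping zero-variance strata changed coverage by no more than about 0.2 points. The shortfall therefore comes from estimating the weights, not from division by zero.

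**Alternatives.** Mantel-Haenszel weights n1 n0/(n1+n0) with the Sato variance covered 94.8-95.1% in the same ORR range, with an interval about 1.5-3% wider. These weights depend only on stratum sizes, so they are finite when every subject responds. They are also the weights in the CMH numerator: with y1 responders of n1 in one arm and y responders of N = n1+n0 overall, sum(y1 - n1 y/N) = sum[(n1 n0/N)(p1 - p0)]. Keeping inverse-variance weights but adding 0.5 to each cell was always defined and covered 94.2-95.4% (equal rates across strata only).

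**The case against.** The strongest reply is that little depends on this formula. The ORR decision, and through it the step to overall survival, rests on the stratified CMH test. The protocol's effect measures for ORR are the odds ratio and the per-arm rates, and its visible text does not ask for a difference. Fixed-effects inverse-variance pooling is a recognised method. The SAP's own definition of the factors leaves no doubt that eight strata are meant. All of this stands, and it is why the point is minor. What it does not answer is that the formula is wrong as printed and incomplete for a foreseeable data pattern.

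A reader might go further in four ways that the documents do not support:

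- That the 12 distorts the estimate. It cannot, since no further strata exist.
- That the undefined weights cause the under-coverage. The shortfall is present where they essentially never occur.
- That the gate to overall survival, or type I error control, is at risk. Neither uses this formula.
- That the coverage loss is large. Simulations with response rates differing across strata under a constant odds ratio gave coverage as low as 86.8%, but that is coverage of a size-weighted difference, a target that the SAP does not specify.

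The SAP also does not commit itself to a faulty variance estimator, because it names none. The defensible criticism there is under-specification. Some nearby text is redacted, so a handling rule in it cannot be excluded.

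**Conclusion.** The point holds as a minor one. The mismatch of 12 against 8 is certain from the documents and has no numerical consequence. The division by zero is certain algebraically for the usual binomial variance. Its frequency cannot be derived from the documents, and the 0% to roughly 13% quoted for ORR of 70-88% rests on an assumed smallest stratum between 47 and 6 per arm; smaller strata or higher rates would raise it. The coverage shortfall, roughly 0.5 to 1 point, does not depend on small strata; it was simulated with response rates equal across strata. The effect is limited to the supplementary ORR difference and its interval, for the review committee's and the investigator's assessments.

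**What to change.** Change the summation limit in SAP 7.5.5 from 12 to 8 in all three places. This is needed whichever weights are used.

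Then preferably estimate the common risk difference with Mantel-Haenszel weights n1 n0/(n1+n0) and the Sato variance. This uses the same stratum weights as the CMH numerator, is defined when a stratum is all responders, and covers about 95%. It is not an exact inversion of the CMH test, so the two can still disagree close to the significance limit.

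If inverse-variance weights are kept, name the variance estimator and pre-specify a rule for zero-variance and empty strata, for example adding 0.5 to each cell.

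The cost is a SAP wording change and a standard software option, with no new data and no design change. The Mantel-Haenszel interval is a few percent wider, about 1.5-3% under the assumptions above.

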7.5.9 Analyses of Overall Survival

Overall survival will be compared between the treatment arms at the interim and final analyses, using a two-sided stratified log-rank test. The stratification factors will be those used in the analysis of PFS.

An O'Brien and Fleming α -spending function will be employed to determine the nominal significance levels for the interim and final analyses.

All analyses performed for PFS (detailed in [section 7.5.1](#)) will be repeated for OS. Supportive analyses 1, 2, 4 and 5 of PFS (detailed in [section 7.5.2](#)) as well as the subset analyses (detailed in [section 7.5.4](#)) will also be repeated for OS. These will be conducted only at the time of the final analysis of OS.

Estimates for 1, 2, 3, 4, and 5-year OS rates will be presented along with their associated 95% CIs when appropriate follow-up time has occurred. These estimates will come from the KM curve and their standard errors (SEs) used in constructing CIs, will be computed using Greenwood's formula¹⁷ and the log-log transformation applied on the survivor function.

7.5.10 Currentness of PFS and OS Data

Time from last tumor assessment to data cut-off in months will be summarized by treatment arm and overall for all randomized subjects. Subjects who have a PFS event will be considered as current for this analysis. The ITT definition of PFS as per IRC will be used for this summary.

In addition Kaplan-Meier plots of time from randomization to post-baseline tumor assessment will be produced by treatment arm for the first twelve assessments.

Currentness of OS data will be summarized in months, by computing the time from "last known alive" date to data cut-off date. Subjects who have a death event will be considered as current for this analysis.

By-subject listings will also be produced to accompany the subject time from last tumor assessment table.

7.5.11 Hierarchy for Testing Secondary Endpoints

A hierarchical procedure will be used to preserve a two-sided family-wise type I error rate of 5% for testing one primary (PFS) and two key secondary endpoints (ORR and OS) in this study.

If there is a statistically significant improvement in PFS, ORR will be compared between treatment arms at the two-sided 5% alpha level. If, and only if, the comparison of ORR is statistically significant, then OS will be compared between treatment arms using a 5% sequential test procedure.

The two QOL secondary endpoints will not be part of the hierarchical testing and will be tested independently of the significance of the other endpoints. Each of the two comparisons will be made at the two-sided type I error of 2.5%.

7.6 Safety

Safety summaries will be based on the treated subject population, grouped by treatment regimen received.

7.6.1 Adverse Events

AEs will be categorized using the most recent version of the MedDRA, by system organ class (SOC) and preferred term. The severity of AEs will be graded using the NCI CTCAE (v 3.0).

On-study AEs are defined as non-serious and serious AEs with an onset date on or after the first dose until 60 days after the last dose. See [Section 8.4](#), Imputing AE Onset Dates, for a discussion of imputation rules for incomplete or missing AE onset dates. If the relationship to study drug is missing, then the AE will be assumed to be related to study drug.

Unless specified otherwise, AEs will be counted only once within each SOC and preferred term, according to their worst CTC grade.

Tables will be sorted by SOC and preferred term, with SOCs ordered by decreasing frequency overall and then alphabetically. Preferred terms will be sorted within SOCs by descending frequency overall and then alphabetically. The sorting will be done based on the total column when arms are presented side-by-side.

Frequency tables of the worst grade of on-study AE will be presented. One summary table will present AEs broken out by individual grade, 1, 2, 3, 4 or 5 along with an Any Grade category. Another one will present AEs by grouped grades as follows “Any, Grade 3-4 and Grade 5.” These summaries will be repeated for on-study drug-related AEs.

A by-subject listing all AEs will be presented.

In addition the following will be presented by treatment arm:

- Frequency of AE before and after cycle 18 for subjects on the Elotuzumab arm
- Exposure-adjusted AE incidence rates (including multiple occurrences of unique events) will be calculated for each SOC and preferred term.

Exposure-adjusted incidence rate per 100 person-years will be used and will be calculated as:

$$100 \times \left(\frac{\text{Total number of unique AEs}}{\frac{\text{subject date of last dose of study drug} - \text{subject date of first dose of study drug} + 60 + 1}{365.25}} \right)$$

and will be displayed along with a count of events. For these additional tables, AEs can be counted multiple times within each SOC and preferred term.

A by-subject listing of unique AEs will be provided.

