3 INVESTIGATIONAL PLAN

3.1 Study Design and Duration

This is a Phase 3, open-label, multi-center trial investigating lenalidomide/ dexamethasone with and without elotuzumab in subjects with newly diagnosed, untreated, symptomatic, measurable myeloma who are ineligible for high-dose therapy plus stem-cell transplantation (SCT) because of age (≥ 65 years) or coexisting conditions.

Eligible subjects will be randomized in a 1:1 ratio to receive either lenalidomide/ dexamethasone (Ld) [Control Arm] or lenalidomide/dexamethasone/elotuzumab (E-Ld) [Investigational Arm]. The randomization will be stratified by:

- Stage of disease (International Staging System 1 - 2 versus 3), see [Appendix 1](#)
- Age (< 75 years old versus ≥ 75 years old)
- ECOG Performance status (0 versus 1 - 2)

Control Arm:

- Lenalidomide:
 - 25 mg po QD Days 1 - 21
- Dexamethasone:
 - 40 mg po weekly Days 1, 8, 15, and 22

Investigational Arm:

- Elotuzumab
 - Cycles 1 - 2: 10 mg/kg IV Days 1, 8, 15, and 22
 - Cycles 3 - 18: 10 mg/kg IV Days 1 and 15
 - Cycle 19 and beyond: 20 mg/kg IV Day 1
- Lenalidomide:
 - 25 mg po QD, Days 1 - 21
- Dexamethasone administered on Days 1, 8, 15 and 22 of each cycle:
 - On weeks when elotuzumab is administered:
 - ◆ 28 mg po (3 - 24 hours prior to start of elotuzumab infusion) AND
 - ◆ 8 mg IV (at least 45 minutes prior to elotuzumab administration)
 - On weeks when no elotuzumab is administered:
 - ◆ 40 mg po

Figure 3.1-1: Study Schema

[figure not shown]

Figure 3.1-2: Dosing Schedule

Control Arm												
Cycle #	1 - 2				3 - 18				19+			
Day # (-1/+3 days)	1	8	15	22	1	8	15	22	1	8	15	22
Lenalidomide - po	←25 mg Days 1 - 21→				←25 mg Days 1 - 21→				←25 mg Days 1 - 21→			
Dexamethasone - po	40 mg	40 mg	40 mg	40 mg	40 mg	40 mg	40 mg	40 mg	40 mg	40 mg	40 mg	40 mg
Investigational Arm												
Cycle #	1 - 2				3 - 18				19+			
Day # (-1/+3 days)	1	8	15	22	1	8	15	22	1	8	15	22
Lenalidomide - po	←25 mg Days 1 - 21→				←25 mg Days 1 - 21→				←25 mg Days 1 - 21→			
Dexamethasone - po	28 mg	28 mg	28 mg	28 mg	28 mg	40 mg	28 mg	40 mg	28 mg	40 mg	40 mg	40 mg
Dexamethasone - IV	8 mg	8 mg	8 mg	8 mg	8 mg	-	8 mg	-	8 mg	-	-	-
Elotuzumab - IV	10 mg/kg	10 mg/kg	10 mg/kg	10 mg/kg	10 mg/kg	-	10 mg/kg	-	20 mg/kg	-	-	-

A cycle is defined as 28 days. Treatment with study drug continues until disease progression, unacceptable toxicity or subject meets other criteria for discontinuation of study drug outlined in [Section 3.5](#)

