Performance Status (ECOG)	X					X			Evaluate prior to dosing
Serious Adverse Event Assessment	X		X*			X	X		Evaluate prior to dosing *Not required in Cycles 19 and beyond
Adverse Events Assessment	X		X*			X	X		Evaluate prior to dosing *Not required in Cycles 19 and beyond
Second Primary Malignancy	X		X			X	X	X	Section 6.7: Performed at 30 and 60 day \pm 1 week EOT follow up visits. After 30 and 60 day EOT visits, second primary malignancy should be assessed every 16 weeks (\pm 2 weeks), or more frequently. Subjects should be followed monthly (if no Progression) or every 16 weeks (if Progression occurred), or more frequently.
Concomitant Medications	X		X*			X	X		Evaluate prior to dosing

Table 5.1-3: Long-term Procedural Outline (CA204006) Cycles 3 and Beyond									
Procedure	Day 1	Day 8	Day 15	Day 22	Rest Days 23 - 28	End of Treatment	Days 30 & 60 Post End of Treatment	Every 16 weeks after progression	Notes
Subsequent Myeloma Therapy						X	X	X	30 and 60 day visits may be performed ± 1 week. After 30 and 60 day EOT visits and EBMT based progression subsequent myeloma should be assessed every 16 weeks (± 2 weeks), or more frequently. Subjects should be followed monthly (if no Progression) or every 16 weeks (if Progression occurred), or more frequently. Start date and end date for second and third line therapy and date of progression after second line therapy will be collected.
Laboratory Tests for Safety									
CBC, differential, platelets	X		X*			X			Section 5.3.4 Can be drawn up to 3 days prior to visit. *Not required in Cycles 19 and beyond
Serum Chemistry	X		X*			X			Section 5.3.4 Can be drawn up to 3 days prior to visit *Not required in Cycles 19 and beyond
Coagulation Tests	X		X*			X			For subjects treated with warfarin thromboembolic prophylaxis *Not required in Cycles 19 and beyond

Table 5.1-3: Long-term Procedural Outline (CA204006) Cycles 3 and Beyond									
Procedure	Day 1	Day 8	Day 15	Day 22	Rest Days 23 - 28	End of Treatment	Days 30 & 60 Post End of Treatment	Every 16 weeks after progression	Notes
Pregnancy Test	X		X*			X	X**		For WOCBP only. Urine tests must have a sensitivity of at least 25 IU/L. Test must be completed on Day 1 and Day 15 within 24 hours prior to dosing. * Not required in Cycles 19 and beyond. However, patients with irregular menstrual cycles must have a pregnancy test every two weeks. ** WOCBP must have a pregnancy test 30, 60, and 90 days Post End of Treatment.

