6 STUDY PERIODS, TREATMENT REGIMENS AND POPULATIONS FOR ANALYSES

6.1 Study Periods

There are three periods in this study: screening, on-treatment and post-treatment follow-up.

Screening: Most screening procedures must be done no more than 14 days prior to randomization. Some exceptions include efficacy assessments and ECGs, which can be done up to 28 days prior to randomization. See Section 5 of the Protocol for full details of study procedures and timings. For analyses purposes data collected within 60 days of randomization and prior to first dose will fall into the screening/baseline period. Site personnel should make every effort to initiate study drug treatment within three days after randomization.

On-Treatment Period: The on-treatment period has three phases: the first two cycles, cycles 3-18, and cycle 19 and beyond. All cycles are 28 days in duration. The first two cycles are characterized by weekly visits, safety assessments, and, in the experimental arm, elotuzumab infusions. Cycles 3-18 are characterized by fortnightly visits, safety assessments and, in the experimental arm, elotuzumab infusions. Cycles 19 and beyond, are characterized by once every 4 weeks visit, safety assessments and, in the experimental arm, elotuzumab infusions. Subjects should have myeloma urine and serum laboratory assessments every four weeks while on treatment until they progress and should have imaging for extramedullary plasmacytomas, if indicated, and at the time of CR/sCR assessment. The timing of the tumor assessments will be independent of dosing. Study treatment ends when the subject progresses, experiences unacceptable toxicity, or withdraws consent.

Follow-up Period: Subjects who discontinue study therapy prior to progression must continue to undergo tumor assessments on the same schedule used in the on-treatment period, regardless of whether they are receiving new anti-myeloma therapy. The only exception to this is if the subject withdraws consent for all study procedures or loses the ability to consent freely.

Follow-up for survival and subsequent myeloma therapy will be conducted every 16 weeks until the subject dies or the study ends.

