- Kaplan-Meier plot of overall survival
- Overall survival Hazard Ratio and 95% CI in Subsets (Forest plot)

Safety:

- Hematologic Laboratory Test Results Summary of Worst Toxicity Grade - SI Units
- Renal and Liver Laboratory Test Results Summary of Worst Toxicity Grade - SI Units
- Chemistry Laboratory Test Results Summary of Worst Toxicity Grade - SI Units
- Other Laboratory Test Results Summary (BUN, DBILI, TPRO)
- Potential Drug Induced Liver Injury Cases Summary - SI Units
- Adverse Event Summary by CTC Grade Combined
- Pre and Post Cycle 19 Adverse Event Summary by CTC Grade Combined
- Serious Adverse Event Summary by CTC Grade Combined
- Adverse Event Leading to Discontinuation Summary by CTC Grade Combined
- Infusion Reaction Summary by Common Terminology Criteria
- Second Primary Malignancy Summary
- Deaths
- Deaths within 60 days of last study drug

Specific tables corresponding to these outputs will be identified in a separate Data Presentation Plan.

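### The before/after Cycle 18 AE table is a crude elotuzumab-arm frequency, so follow-up length, who remains on treatment and fewer AE visits are mixed with the change to 20 mg/kg

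*SAP*

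**What the plan says.** Protocol 3.1 gives elotuzumab as "Cycles 3 - 18: 10 mg/kg IV Days 1 and 15" and then "Cycle 19 and beyond: 20 mg/kg IV Day 1". SAP 7.6.1 lists two additional AE outputs.

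- The first is "Frequency of AE before and after cycle 18 for subjects on the Elotuzumab arm". It states no denominator, no person-time and no restriction to subjects who reach Cycle 19. The lead-in says results are shown by treatment arm, but the item names one arm.
- The second is a rate over all treatment: "Exposure-adjusted incidence rate per 100 person-years will be used". Its denominator runs from first dose to last dose plus 60 days and is not split at Cycle 19.

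The section ends: "For these additional tables, AEs can be counted multiple times within each SOC and preferred term".

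The top-line list in SAP 8.7 has "Pre and Post Cycle 19 Adverse Event Summary by CTC Grade Combined", with no arm named and a differently worded cut point.

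On visits, SAP 6.1 says: "Cycles 19 and beyond, are characterized by once every 4 weeks visit, safety assessments and, in the experimental arm, elotuzumab infusions". Safety visits are weekly in Cycles 1-2 and fortnightly in Cycles 3-18. In Protocol Table 5.1-3 the Day 15 AE and SAE assessments carry the note "Evaluate prior to dosing *Not required in Cycles 19 and beyond".

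**The concern.** A reader will use this table to judge whether AEs became more or less common on the 20 mg/kg schedule. Three other things change at the same point.

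1. **Who is observed.** Treatment stops at progression or unacceptable toxicity, so only subjects who remain on treatment contribute afterwards.
2. **For how long.** The earlier period is capped at 18 cycles. The later one is as long as the data cut allows.
3. **How often they are asked.** Scheduled AE assessments halve.

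A crude frequency cannot separate these from the schedule. The output is on the top-line list, so it may be read early, when later follow-up is shortest.

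**Working it through.** **Plan figures first.** The documents give no power or precision for this table. The inputs borrowed from the PFS design do reproduce: with 482 events, HR 25/33.75 = 0.741 and one O'Brien-Fleming-type look at 338, power is 90.5% (stated 90.5%) and the final level 0.0455 (stated 0.0455). Planned elotuzumab intensity also reproduces: 10 × 2/4 = 20 × 1/4 = 5 mg/kg/week (SAP 7.4.1.3). The weekly dose is unchanged at Cycle 19; dose per infusion and infusion frequency change.

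**Assessments.** Four per cycle in Cycles 1-2, two in Cycles 3-18, one from Cycle 19. The mean over the first 18 cycles is (2×4 + 16×2)/18 = 2.22.

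**Illustration with no schedule effect.** Inputs:
- Cycle 19 starts at T = 18 × 28/30.4375 = 16.56 months.
- Time on treatment is exponential with the planned E-Ld PFS median of 33.75 months: λ = ln 2/33.75 = 0.0205 per month. This is an assumption and the longest case, since treatment stops at progression.
- Accrual is uniform over 31 months; cut-offs are month 41 (Protocol 8.5) and month 60 (Protocol 8.1).
- AE rate is constant at 0.3 per person-year (assumed): r = 0.025 per month. No visit effect is modelled.

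For potential follow-up c, P(c) = r/(λ+r) × (1 − e^(−(λ+r)c)) is the probability of at least one AE. With C the time from entry to cut-off:
- before, all treated: mean of P(min(C, T));
- after, all treated: mean of e^(−λT) × P(C − T), taken as zero if C ≤ T;
- before, subjects reaching Cycle 19: 1 − e^(−rT) = 1 − e^(−0.414) = 33.9%;
- after, subjects reaching Cycle 19: the all-treated value divided by the proportion reaching it, 0.788 × 0.712 = 0.561 at month 41 and 0.712 at month 60.

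| | Month 41 before | Month 41 after | Month 60 before | Month 60 after |
|---|---|---|---|---|
| All treated | 28% | 12% | 29% | 27% |
| Reaching Cycle 19 | 34% | 22% | 34% | 38% |
| Mean months per treated subject | 13.5 | 5.8 | 14.0 | 14.8 |
| Events per treated subject, repeats counted | 0.34 | 0.15 | 0.35 | 0.37 |
| Rate per 100 person-years within period | 30 | 30 | 30 | 30 |

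The event counts are person-time × r, for example 13.5 × 0.025 = 0.34. Counting repeats does not cure the problem; dividing by within-period person-time does, in this model.

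**Range.** Month 41, all treated: rates of 0.1 and 1.0 give 11% vs 5% and 65% vs 29%. Shorter median treatment times of 18 and 24 months (assumed, rate 0.3) give 25% vs 8% and 27% vs 10%. Month 60, subjects reaching Cycle 19: rates of 0.1 and 1.0 give 13% vs 16% and 75% vs 74%; medians of 18 and 24 months give 34% vs 32% and 34% vs 35%. The later period is lower at month 41 in every case tried; at month 60 the sign varies.

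**Selection remains after exposure adjustment.** Take two equal groups with AE rates of 0.3 and 1.2 per year and median treatment times of 45 and 15 months (all assumed), cut at month 60. The within-period rate falls from 69.8 to 56.1 per 100 person-years with no schedule effect. Among Cycle 19 starters the earlier rate is 63.7, so restriction reduces the gap but does not close it. With rates of 0.3 and 0.6 and medians of 45 and 25 months, the fall is 44.3 to 42.3.

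**Arms.** Under the planned medians, the proportion progression-free at 16.56 months is e^(−ln 2 × 16.56/33.75) = 71% on E-Ld and e^(−ln 2 × 16.56/25) = 63% on Ld.

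**The case against.** The table is descriptive: no test is planned and the SAP makes no claim about the schedule. Table detail is left to a separate Data Presentation Plan (SAP 8.7) and a sponsor safety convention (SAP 8.6), which may supply a denominator or a control column. Some sections are redacted. All this stands and limits the weight of the point. It does not alter what the visible text specifies.

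Four stronger readings are tempting and should not be drawn.

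- *An ineffective schedule would look clearly worse by month 60.* Setting 29% against 38% mixes denominators. On one denominator the contrast is 29% vs 27%, or 34% vs 38%, and the latter vanishes or reverses with shorter treatment.
- *Nothing else addresses the new schedule.* SAP 7.6.4 tabulates infusion reactions by cycle and by infusion rate. These are also frequencies, but they bear on the change. This is the only visible summary of AEs overall aimed at it.
- *The control arm undergoes the same selection, so the difference between arms isolates the schedule.* Under the trial's own hypothesis, 71% and 63% are still progression-free at Cycle 19.
- *Half the visits means half the AEs captured.* AEs can be reported spontaneously (Protocol 6) and are assigned by onset date (SAP 7.6.1). Some loss of minor events is plausible; its size is unknown.

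**Conclusion.** The point holds as a cheap improvement. As worded, the table mixes the schedule change with follow-up length, continued treatment and assessment frequency. With no schedule effect it would show about 28% before and 12% after at the interim (34% and 22% among subjects reaching Cycle 19). By month 60 the gap is small and its sign depends on denominator, AE rate and time on treatment. The percentages rest on an assumed constant AE rate and on PFS standing in for time on treatment. The lower later frequency at month 41 held for rates of 0.1 to 1.0 at the planned median and for medians of 18 to 33.75 months at a rate of 0.3. The differing cut-point wording in 7.6.1 and 8.7 is a labelling matter, but it leaves unclear where Cycle 19, the first 20 mg/kg cycle, is counted. Primary and key secondary analyses are untouched.

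**What to change.** In SAP 7.6.1, replace the item with AE summaries split at Cycle 19 Day 1, for both arms, in all treated subjects, as exposure-adjusted rates per 100 person-years. Count events by onset and person-time within each period, and show both. Cycle starts are fixed relative to Cycle 1 Day 1 (Protocol 4.3.3), so the split date exists in both arms: Day 18 × 28 + 1 = 505. Use the same cut and wording in 8.7.

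Add a supportive table in subjects who started Cycle 19, comparing Cycles 13-18 with 19-24. For E-Ld, also show it in those who received elotuzumab in Cycle 19, because Protocol 4.3.3 counts subjects as on therapy after elotuzumab has stopped.

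State the limits with the tables:
- in the supportive table, the earlier period excludes subjects whose AEs ended treatment, while the later period keeps such AEs, which tilts against the later schedule;
- selection into Cycle 19 can differ by arm, so the E-Ld versus Ld contrast is descriptive;
- scheduled assessments halve at the split in both arms;
- the supportive table has fewer subjects.

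The cost is SAP wording, an extended table and one supportive table from data already collected. There is no change to conduct or alpha.
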